# STUDY SYNOPSIS

Title:	The development of a walking test to measure shortness of breath in cardiopulmonary disease							
Short Title:	Measuring exertional breathlessness with the Dyspnea Challenge							
Study sites where project will take	The Prince Charles Hospital, Chermside.							
place:	Griffith University, Gold Coast Campus.							
	Bundaberg Health Promotions, Bundaberg.							
Study Objectives:	
 
To evaluate breathlessness achieved during the 6MWT a surrogate for the dyspnea challenge test.
 
To determine whether we alter the sensitivity of the dyspnea challenge test by altering the grade of treadmill.
 
To compare the metabolic and dyspnea data between differing cardiopulmonary diseases.
 
To assess the responsiveness of the dyspnea challenge to changes in exertional dyspnea experienced post an acute intervention and exercise rehabilitation programs (Pulmonary and Heart Failure rehabilitation programs).
 
							
Study Design:	Prospective, randomised, controlled, single-blind trial							
Study Outcome Measures:	Cardiopulmonary function, exertional breathlessness (dyspnea), test sensitivity, test responsiveness and cardiac function.							
Study Population:	30 moderate-severe COPD patients (GOLD I-IV)							
	30 heart failure patients (NYHA I-III)							
	30 pulmonary hypertension (WHO I-III)							
Number of participants:	90							
Translation to Changes in Clinical Practice:	The results of this study will contribute to the current body of knowledge relating to measuring exertional breathlessness within patient populations. Results will identify whether the dyspnea challenge can be used to test changes in ED in patient groups and validate the use of the dyspnea challenge to assess ED in these patient populations.							
Key Ethical and Safety considerations:	Physical risk, pain or discomfort during activity or other adverse responses associated with the outcome measurements.							

# i. Glossary of Abbreviations, Terms, and Acronyms

Abbreviation, Term, Acronym	Definition (using lay language)							
COPD	Chronic obstructive pulmonary disease							
CPET	Cardiopulmonary exercise testing							
EACPR	European Association for Cardiovascular Prevention and Rehabilitation							
DH	Dynamic Hyperinflation							
ED	Exertional Breathlessness							
EFL	Expiratory Flow Limitation							
EELV	End Expiratory Lung Volume							
GOLD	Global Initiative for Chronic Obstructive Lung Disease							
GU	Griffith University							
IC	Inspiratory Capacity							
ТРСН	The Prince Charles Hospital							
HREC	Human Research Ethics Committee							
PICF	Patient information and consent form							
QoL	Quality of life							
GCHPRP	Gold Coast Health Pulmonary Rehabilitation Program							
TPCHPRP	The Prince Charles Hospital Pulmonary Rehabilitation Program							
6MWT	Six-minute walk test							
ADL	Activity of daily living							
MDP	Multidimensional Dyspnea Profile							
SGRQ	St George Respiratory Questionnaire							
NIRS	Near-infrared spectroscopy							

# • Background

The American Thoracic Society (ATS) defines dyspnea, or breathlessness, as "a subjective experience of unpleasantness and discomfort that is associated with breathing"[1]. Dyspnea occurring during physical activity is known as exertional dyspnea (ED). It is a common symptom of chronic heart and lung disease which inhibits quality of life and impacts the frequency and intensity of physical activity/exercise routines. It is important to note that dyspnea also occurs in health, especially within individuals who are overweight, deconditioned and are aged[2].

As dyspnea is subjective, reported perceptions of this symptom differ in their sensation. Currently, it is recognised that there are three distinct sensations of respiratory discomfort that can be identified using specific descriptors. The feelings are; air hunger, work/effort and tightness. Air hunger refers to an uncomfortable urge to breathe, the kind that is experienced at the end of long breath-hold. Descriptors often used to identify air hunger are "I'm starved for air", "I'm not getting enough air" and are often accompanied by emotional factors such as "frightening" and "like I was going to die". Work/effort sensation is often described as "breathing is difficult", "breathing takes a lot of work", "breathing takes effort". This sensation occurs when there is a self-perceived increase in the effort of breathing. Finally, chest tightness is described as "chest is restricted" or "chest feels tight" and is thought to be unique to asthma sufferers[3].

Individuals with chronic disease, such as chronic obstructive pulmonary disease (COPD)[4, 5], chronic heart failure (CHF)[6, 7] and pulmonary hypertension (PH)[8, 9], all suffer from exertional dyspnea, that which occurs during activity, at levels of exertion in which an agematched control would not. Regarding the distinct sensations, different chronic diseases can be associated with specific sensations. For example, individuals suffering from COPD often select the sensation of work/effort using descriptors such as "my breathing requires more effort or work." Currently, there is no single physiological correlate that can accurately predict exertional dyspnea. Generally, this is because the overall mechanisms that contribute to dyspnea can vary not only between chronic diseases but also between individuals who have been diagnosed with the same condition[10].

Physiologically, it is accepted that ED originates due to an imbalance between ventilatory demand and ventilatory capacity. Specifically, exertional dyspnea may arise through two neurophysiological pathways; 1) a discriminative process that identifies relevant afferent information on respiratory abnormalities and brings them to consciousness and 2) affective processing that labels the short and long-term sensation as unpleasant or threatening[11-13]. The exact origin of these two pathways within differing cardiopulmonary disease is not yet known, this is in part due to the use of inappropriate protocols, the use of a multitude of measurements within studies that have made data comparison difficult, or through the use of measurements that were not designed to specifically measure exertional dyspnea. It is essential to be able to measure ED within patient populations to 1) individually assess potential mechanisms behind each patient's ED symptoms 2) to be able to test and monitor changes in ED pre vs. post interventions and 3) to be able to identify specific mechanisms within a cardiopulmonary group to tailor interventions or treatments.

While there is no 'gold standard' measure of ED, it is most commonly assessed at rest, either by using questionnaires that ask individuals to rate their ED intensity retrospectively; or by performing field-based exercise tests in which ED is not the primary measure and workload is poorly controlled. These limitations are found in routinely used tests, such as the six-minute

walk test (6MWT), restricting the ability to measure change in ED pre vs. post-intervention. The 6MWT is used routinely in both clinical and research settings to assess an individual's functional capacity as it is inexpensive, reproducible, responsive to standardisation and replicates the everyday activity of daily living (ADL) of walking at a self-paced intensity[14]. The 6MWT has routinely been used to assess ED in clinical research with the use of one of the scales from appendices table 1, often the modified BORG (0-10 scale)[15]. Unfortunately, the 6MWT, although a staple in clinical assessment, has been criticised when used for assessing ED. Firstly, the 6MWT is not designed to measure ED; instead, its primary outcome is sixminute walk distance (6MWD), a measure of functional capacity[16], and secondly as stated by Perrault et al. [17]., not standardising the walking speed limits the evaluation of treatments during repeated tests. This is highlighted in Pepin et al [18] in which the 6MWD did not show a significant change after bronchodilation ( $\Delta$  in distance 7m, p>0.005) despite a significant difference in FEV1 of 0.18±0.09L pre vs. post-intervention, (p=<0.001), whereas a set paced exercise test did with a similar change in FEV1 of 0.18±0.12L ( $\Delta$  in distance 144m, p=0.03).

To date there appears to be only a small body of research aimed to specifically develop an exercise test with the primary outcome of measuring ED. These studies have focused on developing short, activity-specific protocols which will elicit ED such as 3 minutes of stepping/walking or upper limb routines designed for people with lower-limb limiting factors. Collectively, these tests have similar issues; firstly, the premise of each design is to regulate workload better, but each test relies heavily on the ability of the participants to coordinate their arm/leg speed with an audio player which may not be appropriate for every individual. A protocol utilising a treadmill, where workload may by regulated with better accuracy, may be more suitable. Secondly, ED is measured discretely at the beginning and end of each 3/5-minute bout of exercise. Although a typical method of recording dyspnea in other field tests (6MWT), evidence exists on the benefit of continually measuring dyspnea during exercise; these include; allowing for the spontaneous changes in ED to be collected and a large number of data to be recorded[19]. Continuous methods of collecting ED scores have been used in more recent research[20]. Finally, the tests do not replicate the activity in which people are most symptomatic, namely; climbing stairs or walking uphill [21-24].

Considering the above limitations Morris et al. [25] recently developed a two-minute treadmill dyspnea challenge in which participants walk at a given speed at an individualised gradient. The aim was to evaluate its repeatability and sensitivity using a high (mean rate: mean gradient of  $4.0\pm0.6$ km/h:  $10\pm2\%$ ) and a low (rate: mean gradient of  $4.0\pm0.6$ km/h:  $6\pm2\%$ ) intensity challenge. The speed was set at 80% of the 6MWT speed and ED was measured continuously using a digital 0-10 scale. They concluded that the dyspnea challenge test is safe, repeatable and sensitive to change in ED. A small sample size is the biggest limitation of this work so far and further study is needed to confirm these findings. The aim of the current research is to continue the development of the dyspnea challenge within COPD patients not only to test its ability to measure ED in a patient population but also to assess the sensitivity of the protocol to changing intensities of exercise. Furthermore, the dyspnea challenge will undergo pre and post intervention testing, both for an acute and longer term interventions, to assess its validity.

# • Study Objectives

#### Aims

The overarching aim of the current study is to develop a 2-minute walk treadmill test to evaluate dyspnea. The primary aims are to assess:

- i. the relationship between 6MWD and exertional dyspnea scores within a 6MWT when compared against exertional dyspnea scores recorded during the dyspnea challenge.
- ii. the sensitivity of the dyspnea challenge to changes in exertional dyspnea via changes to the gradient of the treadmill.
- iii. Compare the exertional dyspnea response to the dyspnea challenge in heart failure, pulmonary hypertension and COPD.
- iv. To assess the responsiveness of the dyspnea challenge to changes in exertional dyspnea experienced post an acute intervention and exercise rehabilitation programs (Pulmonary and Heart Failure rehabilitation programs).

Secondary aims, of the study, will be:

- v. To compare the metabolic cost of the 6MWT and the dyspnea challenge.
- vi. To compare the metabolic cost of the dyspnea challenge between cardiopulmonary disease populations.
- vii. Establish a minimally important difference (MID) for the dyspnea challenge.

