## c. Study Population

Thirty individuals with COPD, thirty with heart failure and thirty with pulmonary hypertension will be recruited into the study if they meet the following criteria:

- A known diagnosis COPD, heart failure or pulmonary hypertension.
- Completed the Gold Coast Health pulmonary or cardiac rehabilitation Program.
- Completed the Prince Charles Hospital pulmonary or cardiac rehabilitation Program.
- Completed the Bundaberg Health Promotions cardiac or pulmonary rehabilitation program.
- Are clinically stable and are on firm, optimised respiratory or cardiac therapy for six weeks before enrolment.
- Global Initiative for Chronic Obstructive Lung Disease (GOLD) categories I-IV.
- New York Heart Association (NYHA) for Heart Failure categories I-III.
- World Health Organisation (WHO) for Pulmonary Hypertension categories I-III.
- Aged  $\geq$  18 years old.

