The DC will be performed be on a treadmill in a temperature-controlled laboratory. Participants will walk on a treadmill for 2-minutes at a speed of 3km/h and a gradient of 4%. Perrault *et al.*, [17] found that 93% of patients suffering from moderate-severe COPD managed to complete a 3-minute walk test at 1.5km/h on a flat surface and that only 84% managed to complete the test at 2.5km/h. The gradient selected was chosen as previous research in 8 participants with mild COPD managed to achieve a 2-minute challenge at between 4-6% gradient[25]. Electrocardiogram (ECG), Heart rate (HR) and oxygen saturation (SpO2) will be monitored continuously using a portable saturation monitor (RAD-5v Masimo Corp, Irvine, CA, USA). Ratings of ED will be participant self-reported every 10 seconds using a 0-10 Numerical Rating Scale (NRS) on a PC-based system with a computer monitor mounted in front of the treadmill. Pulmonary gas exchange (Metamax, Cortex BXB, Lepzig, Germany), cardiac output (Q) (PhysioFlow, Manatec Biomedical, Paris, France) and muscle tissue oxygen saturation (MtO2) (PortaMon Artinis Medical Systems, Einsteinweg, The Netherlands) will be monitored continuously. At the end of the test, sensory and affective measures of ED will be assessed using the MDP[30].

Visit 2 and 3 – During these two visits, participants will perform 2x6MWT and 2xDC. These tests will be performed in a randomised order with 30 minutes of rest in between. 1x6MWT and 1xDC will be performed as above with the same equipment and measures assessed. The other two tests they will be performed without the pulmonary gas exchange measures being assessed. This is to negate the impact of the face mask on self-perceived ratings of exertional dyspnea. During these two tests, ECG, Q, MtO2, HR, SpO2, and blood pressure will be monitored as above. At the end of each test the MDP will be performed.

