#### Part B:

Visit 4-6 – During these visits' participants will perform 6xDC at various gradients of between 3-8% at a speed of 1.5km/h as above. These will be performed in a randomised order. During each test ECG, Q (PhysioFlow, Manatec Biomedical, Paris, France), HR and SpO2 (RAD-5v Masimo Corp, Irvine, CA, USA) will be monitored continuously throughout the test. Ratings of ED will be participant self-reported every 10 seconds using a 0-10 Numerical Rating Scale (NRS) on a PC-based system with a computer monitor mounted in-front of the treadmill. At the end of each test, as per previous tests, the MDP will be completed to assess the sensory and affective components of ED.

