## f. Data Analysis

As subjects act as their own controls, a repeated measures Analysis of Variance statistic will be used for quantitative (physiological) data. All tests will be of a 2-within factor design: time and experimental condition. Dyspnea scores will be measured in the same way. Any non-normal distributed data, highlighted by variance ratio tests, will have a non-parametric Kruskal-Wallis test being applied. Post-hoc analysis will be conducted on any statistically significant data identified post study. Questionnaire data will be analyzed using a Wilcoxon signed rank test. For other comparisons, descriptive statistics alone will be used. Data may be further explored using appropriate parametric or non-parametric correlation statistics. All statistical tests will be done with SPSS software with a significance threshold of P<0.05.

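### Primary aim iii and secondary aim vi compare three diseases, but the stated within-participant model has no disease factor, so both aims fall to an unadjusted comparison that could be misread as a disease effect

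*Protocol*

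**What the plan says.** **Aims.** Under Study Objectives, Aims, primary aim iii is to "Compare the exertional dyspnea response to the dyspnea challenge in heart failure, pulmonary hypertension and COPD". Secondary aim vi asks the same of the metabolic cost of the challenge.

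**Groups.** Under Study Population, "Thirty individuals with COPD, thirty with heart failure and thirty with pulmonary hypertension will be recruited into the study". Membership follows from diagnosis. The entry criteria set a minimum age of 18 and no matching on age, sex or weight.

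**Randomisation.** The study is labelled randomised and controlled, but what is randomised is the order of tests within a participant. For Visits 2 and 3: "These tests will be performed in a randomised order with 30 minutes of rest in between". Parts B and C likewise randomise order.

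**Treadmill settings.** In Part A, "Participants will walk on a treadmill for 2-minutes at a speed of 3km/h" with a 4% gradient. In Part B, "participants will perform 6xDC at various gradients of between 3-8% at a speed of 1.5km/h as above". Neither setting is tailored to the individual.

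**Known influences.** The Background notes that "dyspnea also occurs in health, especially within individuals who are overweight, deconditioned and are aged".

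**Analysis.** The Data Analysis section adopts repeated-measures analysis of variance because participants serve as their own controls. It gives all tests two within-participant factors (time and experimental condition) and treats dyspnea scores likewise. Non-normal data go to a Kruskal-Wallis test. For the remainder, "For other comparisons, descriptive statistics alone will be used".

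**The concern.** Own-control reasoning works for comparing two tests, several gradients, or before and after an intervention in the same person. It cannot work for aims iii and vi, because nobody contributes data to more than one diagnosis. The stated model has no term for the quantity that these aims ask about.

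What remains in the section is either description or a rank test, and neither takes a covariate. The cohorts may differ in age, weight and fitness, which the protocol itself links to breathlessness. A raw contrast would then mix those differences with disease. At stake is the interpretation of one primary and one secondary aim; the within-participant aims are not affected.

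**Working it through.** **1. The plan's own figure.** 3 cohorts × 30 = 90, which matches the Synopsis. No standard deviation, effect size or power is given, so there is no sample-size calculation to reproduce.

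**2. Can the stated model answer the aims?**

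| Element | Aims iii and vi need | Data Analysis provides |
|---|---|---|
| Disease | between-participant factor | none |
| Factors in the model | disease, with any within-participant terms | time and condition, both within participant |
| Fallback | adjusted contrast | Kruskal-Wallis or description, no covariate |

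The answer is no. Suppose that response in aim iii means the change across gradients. Additive personal offsets then cancel within each participant, but comparing those changes between diseases still needs a disease-by-gradient term, which is also absent.

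**3. Load at common settings.** Lifting power = mass × 9.81 × vertical speed. The body masses are examples.
- Part A: 3 km/h = 50 m/min; × 0.04 = 2 m/min. Power per kg = 9.81 × 2/60 = 0.327 W. This gives 19.6 W at 60 kg, 22.9 W at 70 kg, 26.2 W at 80 kg and 32.7 W at 100 kg. From 60 to 100 kg the rise is 32.7/19.6 − 1 = 67%.
- Part B: from 60 to 100 kg, 7.4 to 12.3 W at 3%, and 19.6 to 32.7 W at 8%.

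Absolute load rises in proportion to mass. Load per kilogram is the same for everyone.

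**4. Illustration in points.** These inputs are assumptions, not figures from the protocol: 0.03 points per year of age, 0.02 to 0.04 points per kg, cohorts 10 years and 10 kg apart, SD 2, a two-sided 5% test and no true disease effect.
- SE = 2 × √(2/30) = 0.516.
- Older cohort also heavier: shift = 0.3 + (0.2 to 0.4) = 0.5 to 0.7 points. Divided by the SE this is 0.97 to 1.36, and the rejection rate is about 16% to 27%.
- Older cohort lighter: shift = 0.3 − (0.2 to 0.4) = +0.1 to −0.1 points. The rejection rate is at most about 5.4%.

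**5. Illustration in SD units.** Bias = r × g, where r is the within-group correlation of a covariate with dyspnea and g is the largest gap between cohort means in SD. Both are assumed.

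| r | g | Bias (SD) | Pairwise rejection, unadjusted | Three-group ANOVA, unadjusted | Three-group, adjusted |
|---|---|---|---|---|---|
| 0.2 | 0.5 | 0.10 | 6.7% | 5.4% | 4.5% |
| 0.3 | 1.0 | 0.30 | 21.3% | 16.7% | 5.2% |
| 0.5 | 1.5 | 0.75 | 82.8% | 73.0% | 4.9% |

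The pairwise column is a normal approximation for the two cohorts furthest apart, with 30 per group. The three-group columns come from 3,000 simulated trials per row, with cohort means of the covariate at 0, g/2 and g. Over all twelve settings run (r 0.2 to 0.5, g 0.5 to 1.5) the adjusted rate was 4.5% to 5.6%. The simulation has one covariate, linear and measured without error, so it shows what adjustment does when the adjustment model is right.

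**6. Scale.** With 30 per group, the pairwise difference detectable with 80% power is (1.96 + 0.84) × √(2/30) = 0.72 SD. Only the largest bias in the table exceeds it.

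**The case against.** **A covariate list belongs in a statistical analysis plan.** This is fair, and its absence alone would not be a finding. But the protocol goes further and fixes a model and a rationale for all tests. A later plan that follows it cannot estimate a disease difference, and one that does estimate it must depart from the protocol. That part of the point stands.

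**The protocol draws no disease conclusion.** This is correct. Aim iii only compares, no hypothesis concerns differences between diseases, and the section on translation claims none. A reader might infer that cohort differences will be reported as disease effects. The text supports only that they could be.

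**There may be no test to inflate.** If the aim falls under "For other comparisons, descriptive statistics alone will be used", a false-positive rate does not apply. A reader might take 16% to 27% as the error rate of this trial. It is not: every input is assumed, and opposing gaps bring it back to about 5%.

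**The workload is not a single one.** One fixed setting describes Part A only. Part B has six gradients at another speed, and Study Procedure ties aim iii to no visit. What stands is that the settings are common to all participants.

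**Body mass is debatable.** Load per kilogram is equal for all, the documents do not say which scale matters, and mass may partly reflect disease. This argues for showing both estimates rather than for leaving mass out.

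**Covariates and site.** The Background names deconditioning, which the proposed covariates do not capture, and it does not name sex, which rests on general reasoning. A site effect is possible, but nothing in the documents shows one. Where site and disease overlap, a site-adjusted main estimate would be imprecise.

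**Conclusion.** The point holds in a limited form. For aims iii and vi the stated within-participant model cannot estimate the between-disease difference, and its own-control rationale does not apply. What is left is unadjusted, although the protocol itself names influences on breathlessness that may differ between cohorts. This follows from the text and needs no assumption.

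The direction and size of any bias cannot be known from the documents. The 67% spread in absolute lifting power between 60 and 100 kg follows from the settings, but the masses are examples and the spread disappears per kilogram. The rejection rates, from about 5% to well above it, show only that the bias could matter with 30 per group. The documents do not support saying that the comparison will be misread, or that it has a particular error rate. The protocol should be corrected because a primary aim is affected and the correction is cheap.

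**What to change.** In Data Analysis, for aims iii and vi:

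1. Name disease as a between-participant factor, and limit the own-control rationale to the within-participant aims.
2. Report each between-disease difference with its 95% confidence interval, adjusted for age, sex and body mass, beside the unadjusted difference.
3. Use adjustment for site as a sensitivity analysis only.
4. State that the comparison is observational and is not protected by randomisation, which covers test order alone.

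In the Visit 1 procedures, list body mass. It may already be part of the health screen, whose contents are not given.

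**Cost.** A few sentences, at most one weight reading per participant and a few degrees of freedom; the total of 90 does not change. Adjusting for body mass may remove some of what disease itself causes, which is why both estimates are shown. Confounding by deconditioning would remain and should be acknowledged.
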